3.1 Primary analysis

To test the null hypothesis that the MMR rate at 24 weeks is equal in the two treatment arms, based on two-sided 5% level of significance and with 90% power, 222 patients will be needed in total (i.e. 148 patients in the asciminib arm and 74 patients in the bosutinib arm based on 2:1 randomization allocation). The calculations were made using the software package PASS (2008).

It is assumed that asciminib leads to a 20% improvement in the MMR rate at 24 weeks over bosutinib from 15% to 35% which corresponds to an odds ratio of 3.05. The assumed bosutinib MMR rate of 15% at 24 weeks is based on previous trials evaluating bosutinib therapy ([Kuoury et al. 2012], [Gambacorti-Passerini et al. 2014], [García-Gutiérrez et al. 2015]).

3.2 Power for analysis of key secondary variables

If the primary analysis of MMR rate at 24 weeks is statistically significant, then the key secondary endpoint MMR rate at 96 weeks will be tested, with the overall alpha controlled at the 5% two-sided level using a gatekeeping strategy.

Table 3-1 below summarizes the treatment effects of the key secondary endpoint which can be detected with 80% and 90% power, based on the specified assumptions regarding the bosutinib effect. The calculations were made using the software package PASS (2008).

Table 3-1 Detectable effect sizes for key secondary endpoint

Endpoint	Anticipated effect with bosutinib	2-sided alpha	Power	Detectable effect size [§]
MMR rate at 96 weeks	30% [*]	0.05	90%	≥ 23%
			80%	≥ 20%

*: [Gambacorti-Passerini et al. 2014], Figure 1D.

§: Absolute difference from the anticipated effect with bosutinib.

For MMR rate at 96 weeks, if the anticipated effect with bosutinib is 30%, then the given sample size with 2-sided alpha=0.05 would allow to detect an absolute difference of at least 23% (i.e. MMR rate at 96 weeks with asciminib is at least 53%) for 90% power and of at least 20% (i.e. MMR rate at 96 weeks with asciminib is at least 50%) for 80% power.

4 Change to protocol specified analyses

Pharmacokinetic analysis set: Removal of the condition related to vomiting to consider a concentration evaluable as the occurrence and time of vomiting is not collected in the CRF.

The estimand language was implemented in sections 2.5 and 2.6. Then, the PPS and analyses based on PPS were removed.

The subgroup considering historical BCR-ABL1 mutations was removed as not considered clinically relevant.

A definition for loss of CHR was provided.

Definition of loss of MMR: removed any reference to confirmation of CHR and CCyR as confirmation of CHR and CCyR was not mandated by protocol and was therefore not performed in practise.

The following analyses were added:

ECOG status, time to event analyses for duration of MMR and CCyR, exposure adjusted AE incidence and yearly AE incidence, COVID-19 related sensitivity analyses.

5 Appendix

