2.6.2 Statistical hypothesis, model, and method of analysis

The null hypothesis is that there is no difference between the treatment groups with respect to MMR rate at 96 weeks. Following a gatekeeping procedure to control the overall alpha level, only if the primary endpoint is significant, formal statistical testing of the key secondary endpoint with two-sided 5% level of significance will be performed using the CMH chi-square

test, stratified by the randomization stratification factor, i.e. cytogenetic response status (MCyR vs no MCyR) at screening.

MMR rate and its 95% confidence interval based on the Pearson-Clopper method will be presented by treatment group. The 95% confidence interval for the difference in MMR rate between treatment groups will be provided using the Wald method. The Mantel-Haenszel estimate of the common risk difference and the corresponding 95% confidence interval will also be presented.

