2.15 Interim analysis

No formal interim analysis is planned for this trial.

Three to four analyses are planned with the analysis data cut-off dates and the scope of analyses as follows:

- **24-week Primary analysis:** Formal testing of the primary endpoint with full alpha will be performed. Analyses of other efficacy endpoints at and by 24 weeks will also be performed.
- **96-week analysis:** Formal statistical testing of the key secondary endpoint will be performed with $\alpha = 0.05$ (two-sided) only if the primary endpoint (i.e. MMR rate at 24 weeks) is significant. Otherwise, no statistical testing will be performed, and any analysis will be considered exploratory. Analyses of other efficacy endpoints will also be performed.
- **End of study treatment (EOsT) analysis (if required):** similar to the 96-week analysis without formal statistical testing.

NOTE: This analysis may be conducted at the same time as 96-week analysis.

- **5-year PFS/OS update analysis:** PFS and OS.

In addition, DMC safety analyses will be conducted. Prior to the database lock for the primary analysis, tables and figures aggregated by treatment arm for safety data review by the DMC or for other reporting activities will be produced by an independent statistician and independent statistical programmers.

3 Sample size calculation

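### Table 3-1 gives the power of the Week 96 MMR test alone; with the written Week 24 gate, the chance of a formal Week 96 claim is about 83-86% and 76-79% (82-83% and 74% under independence), not 90% and 80%

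*Combined protocol and SAP*

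**What the plan says.** SAP section 3.1 sizes the trial on MMR at Week 24: "based on two-sided 5% level of significance and with 90% power, 222 patients will be needed in total". The 2:1 split puts 148 on asciminib and 74 on bosutinib. The assumed rates are 15% on bosutinib and 35% on asciminib.

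Section 2.6.2 sets the testing order: "only if the primary endpoint is significant, formal statistical testing of the key secondary endpoint with two-sided 5% level of significance will be performed". Sections 2.15 and 5.6.2 repeat the rule. Section 2.15 adds that without a significant primary result there is no formal test and the Week 96 analysis is exploratory.

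Section 3.2 first restates the gate and then gives the power in Table 3-1 and the text below it. Taking a 30% rate on bosutinib and a two-sided alpha of 0.05, it claims that the trial can find "an absolute difference of at least 23% (i.e. MMR rate at 96 weeks with asciminib is at least 53%) for 90% power". The second row of the table pairs a 20-point difference (50% on asciminib) with 80% power. No gate-adjusted power is given, and no assumption about how Week 24 and Week 96 responses are associated. The same statement stands in the first SAP (25-Aug-2017), in amendment 3.0 (7-Aug-2020, before the primary database lock) and in addendum 1.0 (14-Oct-2020, after it).

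**The concern.** A formal Week 96 claim needs two significant results. The inputs to Table 3-1 are the Week 96 rates, alpha and the sample size. None of them reflects the chance of failing at the first step. A reader who takes 90% as the probability that this design delivers the Week 96 claim at a 23-point difference is given a figure that the written procedure does not have under the plan's own assumptions. Week 96 MMR is the only endpoint besides the primary that is tested formally, so its stated power should match the rule that governs it.

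**Working it through.** **Inputs from the SAP.** 74 bosutinib and 148 asciminib patients, two-sided alpha 0.05; Week 24 MMR 15% vs 35% (section 3.1); Week 96 MMR 30% vs 53% or 50% (section 3.2).

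**Assumption not in the SAP.** Persistence s = P(MMR at Week 96 | MMR at Week 24), the same in both arms, from 0.6 to 1.0. Independence is shown as a reference case.

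**Step 1: reproduce the plan's figures.** Pooled two-proportion test without continuity correction:

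power = Φ[(d − 1.96·SE0) / SE1], where SE0 uses the pooled rate and SE1 the separate rates.

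| Comparison | d | SE0 | SE1 | Power |
|---|---|---|---|---|
| Week 24, 35% vs 15% | 0.20 | 0.0642 | 0.0571 | 90.3% |
| Week 96, 53% vs 30% | 0.23 | 0.0709 | 0.0672 | 91.2% |
| Week 96, 50% vs 30% | 0.20 | 0.0706 | 0.0673 | 82.1% |

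The same formula returns 74 + 148 = 222 for the primary. Exact enumeration of the chi-square test gives 90.6%, 91.2% and 82.1%. Solving for exactly 90% and 80% at Week 96 gives differences of 22.5 and 19.5 points, which round up to the printed 23 and 20. Table 3-1 is therefore the power of one ungated Week 96 test.

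**Step 2: apply the gate.** If the two test results were independent, the joint probability would be the product:
- 23 points: 0.9033 × 0.9122 = 82.4%
- 20 points: 0.9033 × 0.8205 = 74.1%

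Patient-level simulation with independent responses gives 82.6% and 74.2-74.5%.

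With persistence s, the probability of MMR at both visits in an arm is s × (Week 24 rate), and the marginal rates stay fixed. Simulation with 400,000 trials per setting, both tests significant in favour of asciminib:

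| Persistence | 53% vs 30% | 50% vs 30% |
|---|---|---|
| 0.6 | 83.3% | 75.6% |
| 0.7 | 83.8% | 76.3% |
| 0.8 | 84.3% | 77.0% |
| 0.9 | 85.0% | 77.8% |
| 1.0 | 85.7% | 78.9% |

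In each arm the Week 24 rate is below the Week 96 rate, so s = 1.0 is the strongest association these rates allow. Even there, both rows are below print.

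**Step 3: size of the gap.**
- 23-point row: risk of missing the claim runs from 100 − 85.7 = 14.3% to 100 − 82.4 = 17.6%, against the stated 10%.
- 20-point row: shortfall against print runs from 80 − 78.9 = 1.1 to 80 − 74.1 = 5.9 points.

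**Step 4: sensitivity to the Week 24 effect.** The bosutinib rate stays at 15%. Ranges run from independence to full persistence.

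| Week 24 asciminib rate | Joint power, 23 points | Joint power, 20 points |
|---|---|---|
| 35% (plan) | 82-86% | 74-79% |
| 38% (illustrative) | 88-90% | 79-81% |
| 40% (illustrative) | 89-91% | 81-82% |

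**The case against.** The strongest reply is that nothing is miscalculated. Table 3-1 is headed as detectable effect sizes, it reproduces as stand-alone power (slightly above print), and the gate is stated immediately before it. It can be read as the power of the Week 96 test once that test is performed. On that reading, conditional power given a significant Week 24 result is about 92-95% and 83-87% over the persistence range, so the printed figures would be cautious. This stands in part: a reader might infer an arithmetic error in the table, and there is none. But nothing labels the figures as conditional on the gate, and they match the unconditional stand-alone calculation.

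Second, the size of the gap depends on inputs that section 3.2 does not supply: a persistence figure, and a Week 24 effect paired with the Week 96 effect. This also stands. At 38-40% vs 15% the gap largely closes. It does not close at 35% vs 15%, the rate on which the trial was sized.

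Third, addendum 1.0 postdates the primary database lock, so a prospective gate probability no longer informs a decision in that version. True, but the same text stood in the versions finalised before the lock.

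A reader might also infer that the risk of missing the 23-point claim is doubled, or that the gate's own power of about 90% alone rules out the printed 90%. Neither is supported. The risk is 1.4 to 1.8 times the stated one, and a ceiling near 90% does not by itself exclude 90%. The shortfall comes from the joint calculation.

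**Conclusion.** The point holds as one of labelling and completeness. The printed 90% and 80% are the power of the Week 96 test alone. The gated procedure reaches about 83-86% at 23 points and 76-79% at 20 points for 60-100% persistence, and about 82-83% and 74% under independence.

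These figures rest on true Week 24 rates of 35% vs 15%, equal persistence in both arms, and an unstratified test. The planned analysis is a stratified CMH test, but the SAP gives no stratum rates with which to refine the calculation. The protocol body was not available for this check, so a joint power stated there cannot be excluded.

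It would be wrong to conclude that the trial is undersized or that error control is affected. The sample size was set by the primary endpoint, and the fixed-sequence rule controls alpha as intended.

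**What to change.** In section 3.2 and Table 3-1, label the 90% and 80% figures *power of the Week 96 test alone, not allowing for the Week 24 gate*. Beside them, add the probability of a significant result on both tests as a range: about 83-86% (23 points) and 76-79% (20 points) for 60-100% persistence, and about 82-83% and 74% under independence. State the Week 24 rates (35% vs 15%) and the persistence range as assumptions. No single persistence value should become the planning figure unless a source is given. A line for a larger Week 24 effect would show how far the gap depends on it.

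The cost is a few lines of SAP text and one short simulation. Enrolment, alpha and the test do not change. The only downside is a somewhat less favourable stated figure.

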5.1 Imputation rules

5.1.1 Study drug

The following rules should be used for the imputation of the dose end date for a given study treatment component.

Scenario 1: If the dose end date is completely missing and there is no EOT page and no death date, the patient is considered as on-going:

The patient should be treated as on-going and the cut-off date should be used as the dose end date.

Scenario 2: If the dose end date is completely missing and the EOT page is available:

The EOT completion date should be used.

- All other cases should be considered as a data issue and the statistician should contact the data manager of the study.
- After imputation, compare the imputed date with start date of treatment, if the imputed date is < start date of treatment:

Use the treatment start date

Patients with missing start dates are to be considered missing for all study treatment component related calculations and no imputation will be made. If start date is missing then end-date should not be imputed.

5.1.2 AE, ConMeds and safety assessment date imputation

The imputations specified in this section are only used for analyses of time to and duration of AEs and concomitant medications.

Table 5-1 Imputation of start dates (AE, CM) and assessments (LB, EG, VS)

Missing Element	Rule
day, month, and year	
 No imputation will be done for completely missing dates
day, month	
 If available year = year of study treatment start date then 
 If stop date contains a full date and stop date is earlier than study treatment start date then set start date = 01JanYYYY Else set start date = study treatment start date. If available year > year of study treatment start date then 01JanYYYY If available year < year of study treatment start date then 01JulYYYY
day	
 If available month and year = month and year of study treatment start date then 
 If stop date contains a full date and stop date is earlier than study treatment start date then set start date= 01MONYYYYY. Else set start date = study treatment start date. If available month and year > month and year of study treatment start date then 01MONYYYYY If available month and year < month year of study treatment start date then 15MONYYYYY

Table 5-2 Imputation of end dates (AE, CM)

Missing Element	Rule (* = last treatment date plus 30 days not > (death date, cut-off date, withdrawal of consent date))
day, month, and year	
 Completely missing end dates (incl. ongoing events) will be imputed by the end date of the on-treatment period*
day, month	
 If partial end date contains year only, set end date = earliest of 31DecYYYY or end date of the on-treatment period *
day	
 If partial end date contains month and year, set end date = earliest of last day of the month or end date of the on-treatment period*

Any AEs and ConMeds with partial/missing dates will be displayed as such in the data listings.

Any AEs and ConMeds which are continuing as per data cut-off will be shown as 'ongoing' rather than the end date provided.

5.1.2.1 Other imputations

Incomplete date of initial diagnosis of cancer

Missing day is defaulted to the 15th of the month and missing month and day is defaulted to 01-Jan.

Stratum reported in the CRF

This will be derived from the Bone Marrow Aspirate data recorded in the corresponding eCRF pages at baseline. In some case the baseline sample may be missing or not evaluable (i.e. <20 metaphases).

The following imputation rule will be applied to derive the missing or non evaluable values:

- Major cytogenetic response (MCyR) (0 to 35% Ph+ metaphases) will be assumed if BCR-ABL1 levels $\leq 10\%$ (IS).

Rationale:

ELN 2013 recommendations are providing treatment milestones with response categories for cytogenetic and molecular response, which we can refer to for the imputation:

6 mo	BCR-ABL1 <1% and/or Ph+ 0	BCR-ABL1 1-10% and/or Ph+ 1-35%	BCR-ABL1 >10% and/or Ph+ >35%
------	---------------------------------	---------------------------------------	-------------------------------------

MCyR is roughly corresponding to BCR-ABL1 levels $\leq 10\%$ (IS) (Ross et al 2009).

5.2 AEs coding/grading

Adverse events are coded using the latest available version of Medical dictionary for regulatory activities (MedDRA) terminology.

AEs will be assessed according to the Common Terminology Criteria for Adverse Events (CTCAE) version 4.03.

The CTCAE represents a comprehensive grading system for reporting the acute and late effects of cancer treatments. CTCAE grading is by definition a 5-point scale generally corresponding to mild, moderate, severe, life threatening, and death. This grading system inherently places a value on the importance of an event, although there is not necessarily proportionality among grades (a grade 2 is not necessarily twice as bad as a grade 1).

5.3 Laboratory parameters derivations

Grade categorization of lab values will be assigned programmatically as per NCI Common Terminology Criteria for Adverse Events (CTCAE) version 4.03. The calculation of CTCAE grades will be based on the observed laboratory values only, clinical assessments will not be taken into account. The criteria to assign CTCAE grades are given in Novartis internal criteria

for CTCAE grading of laboratory parameters (embedded below). The latest available version of the document based on the underlying CTCAE version v4.03 at the time of analysis will be used. For laboratory tests where grades are not defined by CTCAE v4.03, results will be graded by the low/normal/high (or other project-specific ranges, if more suitable) classifications based on laboratory normal ranges.

A severity grade of 0 will be assigned for all non-missing lab values not graded as 1 or higher. Grade 5 will not be used. For laboratory tests that are graded for both low and high values, summaries will be done separately and labelled by direction, e.g., sodium will be summarized as hyponatremia and hypernatremia.

EASE LAB - CTC
grades in Novartis Or

Imputation Rules

Hematology

Immature cells (promyelocytes, myelocytes, metamyelocytes and blasts) will not be displayed in shift tables and will only be listed.

Immature cells are manually counted only if anomalies are detected during the automatic testing. Therefore, when the automatic testing was performed but no data is transferred for immature cells, this means there was no immature cells and their values can be imputed to 0. Note that there should not be any imputation in case the automatic testing was not performed or the test of immature cells is present with missing value in the database (this would mean the test was to be performed but couldn't).

CTCAE grading for blood differentials is based on absolute values. However, this data may not be reported as absolute counts but rather as percentage of white blood cells (WBC).

If laboratory values are provided as '<X' (i.e. below limit of detection) or '>X', prior to conversion of laboratory values to SI unit, these numeric values are set to X.

The following rules will be applied to derive the WBC differential counts when only percentages are available for a xxx differential

$$\text{xxx count} = (\text{WBC count}) * (\text{xxx \%value} / 100)$$

The following rules will be applied to derive the WBC differential percentages when only differential counts are available for a xxx differential

$$\text{xxx \%value} = (\text{xxx count} \times 100) / \text{WBC count}$$

Further derivation of laboratory parameters might be required for CTCAE grading. For instance, corrected calcium can be derived using the reported total calcium value and albumin at the same assessment using the following formula:

$$\text{Corrected Calcium (mmol/L)} = \text{Calcium (mmol/L)} + 0.02 (40 - [\text{Albumin (g/L)}])$$

For calculation of laboratory CTCAE grades 0 and 1, the normal range for derived corrected calcium is set to the same limits (in mmol/L) as for calcium.

CTCAE grades for the derived absolute WBC differential counts (neutrophils, lymphocytes) and corrected calcium will be assigned as described above for grading.

Biochemistry

In order to avoid double reporting of the same information, all available values for BUN and UREA will be reported under the parameter name BUN (mmol/L) in listing using the following conversion rule: UREA (mmol/L)=2.14 BUN (mmol/L) ([Lamb E et al 2012]).

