Recruitment period extension has been reflected in the VES table. Study length has changed with introduction of switch option for patients failing bosutinib treatment.

Patients enrolling in this trial will present a high disease burden after failure of previous therapies. Myelosuppression during TKI targeted treatment is a very common effect observed due to the suppression of the leukemic clone; this effect is also extended to hematopoiesis of

stem cells and progenitors (Steggmann et al 2016). For this reason, the recovery period for cytopenias has been extended from 28 to 42 days in order to allow for sufficient time to recover from suppression and to re-populate the bone marrow.

The biomarker sampling profile has been revised to remove the gene expression profile in leukemic stem cells in both blood and bone marrow due to technical limitations. In addition, there is currently no validated assay available.

A clarification has been made to how the tests for blood urea and Blood Urea Nitrogen (BUN) are noted. The text "blood urea, Blood Urea Nitrogen (BUN)" has been revised to "blood urea or Blood Urea Nitrogen (BUN)" in order to note that either test is permitted.

Changes to the protocol

Changes to specific sections of the protocol are shown in the track changes version of the protocol using strike through red font for deletions and red underline for insertions.

- Change of the purpose of the study by decreasing the requirement of BCR-ABL1 ratio \geq 1% IS to BCR-ABL1 ratio $>$ 0.1% IS at the time of screening for patients with intolerance:
 - Protocol summary.
 - Section 2.1 Study rationale and purpose.
 - Section 4.1 Description of study.
 - Section 5.2 Inclusion criteria.
 - Section 10.5.2 Other secondary efficacy objectives.
- Change of the study design by introducing the switch to asciminib option for patients experiencing treatment failure on bosutinib treatment:
 - Protocol summary.
 - Section 2.2 Rationale for the study design.
 - Section 4.1 Description of study.
 - Figure 4-1 Schematic of Study Design.
 - Addition of Section 4.1.1 Study treatment switch from bosutinib to asciminib
 - Section 4.3 Definition of end of study.
 - Section 6.1.5 Treatment duration
 - Section 6.7.3.2 Study drug accountability.
 - Section 7 Visit schedule and assessments:
 - Addition of Table 7-2 Visit evaluation schedule (study treatment switch phase).
 - Addition of Section 7.1.2.2 Conditions to be fulfilled for asciminib switch.
 - Section 7.1.5 Visit windows.

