The following rules will be applied to derive the WBC differential percentages when only differential counts are available for a xxx differential

$$\text{xxx \%value} = (\text{xxx count} \times 100) / \text{WBC count}$$

Further derivation of laboratory parameters might be required for CTCAE grading. For instance, corrected calcium can be derived using the reported total calcium value and albumin at the same assessment using the following formula:

$$\text{Corrected Calcium (mmol/L)} = \text{Calcium (mmol/L)} + 0.02 (40 - [\text{Albumin (g/L)}])$$

For calculation of laboratory CTCAE grades 0 and 1, the normal range for derived corrected calcium is set to the same limits (in mmol/L) as for calcium.

CTCAE grades for the derived absolute WBC differential counts (neutrophils, lymphocytes) and corrected calcium will be assigned as described above for grading.

Biochemistry

In order to avoid double reporting of the same information, all available values for BUN and UREA will be reported under the parameter name BUN (mmol/L) in listing using the following conversion rule: UREA (mmol/L)=2.14 BUN (mmol/L) ([Lamb E et al 2012]).

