2.8.3 Laboratory data

Grading of laboratory values will be assigned programmatically as per National Cancer Institute (NCI) Common Terminology Criteria for Adverse Events (CTCAE) version 4.03. The calculation of CTCAE grades will be based on the observed laboratory values only, clinical assessments will not be taken into account. CTCAE Grade 0 will be assigned for all non-missing values not graded as 1 or higher. Grade 5 will not be used. Details of CTCAE grading and imputation rules are presented in [Appendix 5.3](#).

For laboratory tests where grades are not defined by CTCAE v4.03, results will be categorized as low/normal/high based on laboratory normal ranges.

On analyzing laboratory data, all sources (central and local laboratories) will be combined. The summaries will include all assessments available for the lab parameter collected no later than 30 days after the last study treatment administration date.

The following summaries will be produced on the Safety set separately for hematology and biochemistry laboratory data (by laboratory parameter and treatment):

- Worst post-baseline CTCAE grade (regardless of the baseline status). Each subject will be counted only for the worst grade observed post-baseline in the on-treatment period.
- Shift tables using CTCAE grades to compare baseline to the worst on-treatment value.
- For laboratory tests where CTCAE grades are not defined, shift tables using the low/normal/high/(low and high) classification to compare baseline to the worst on-treatment value.

The same summaries will be produced on the Switch Analysis Set for the on-switched treatment period.

The following listings will be produced separately for hematology and biochemistry for the laboratory data:

- Listings of all laboratory data, with CTCAE grades and classification relative to the laboratory normal range. Lab data collected during the post-treatment period will be flagged.
- Listing of all CTCAE grade 3 or 4 laboratory toxicities

Liver function parameters

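### The urea-to-BUN rule applies the mass-unit factor 2.14 to values in mmol/L, so urea results listed as BUN are more than halved and raised values can look normal.

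*Combined protocol and SAP*

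**What the plan says.** The Biochemistry paragraph of SAP Section 5.3 aims to avoid listing the same information twice. It states that every urea and BUN result is to be "reported under the parameter name BUN (mmol/L) in listing using the following conversion rule: UREA (mmol/L)=2.14 BUN (mmol/L", closing the bracket and citing a source. The identical line stands in SAP amendment 3.0 and in addendum 1.0.

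Three other places bear on how the listed value will be read:

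- The rationale of the protocol amendment that introduced the switch to asciminib changes the wording for blood urea and BUN "in order to note that either test is permitted". Results of both kinds can therefore be in the database.
- SAP Section 2.8.3 combines central and local laboratory data and plans "Listings of all laboratory data, with CTCAE grades and classification relative to the laboratory normal range".
- The same section adds: "For laboratory tests where grades are not defined by CTCAE v4.03, results will be categorized as low/normal/high based on laboratory normal ranges".

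For corrected calcium, Section 5.3 says which normal range applies to the derived value. It says nothing comparable for a urea result renamed as BUN.

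**The concern.** A conversion factor is tied to its units. The factor 2.14 is familiar for turning a mass concentration of urea nitrogen into a mass concentration of urea. The SAP attaches it to mmol/L on both sides, where the mass ratio has no role.

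A programmer who follows the text will divide every molar urea result by 2.14 and list it beside BUN results that were measured directly and left unchanged. Three things then go wrong:

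- The listed number is wrong for every converted sample.
- Two samples with the same urea content show different values according to which test was run, so an apparent change within a patient may be only a change of test.
- If the low/normal/high class is taken from the converted value against an unconverted range, a raised urea is shown as normal.

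The rule was meant to put one quantity on one scale. As written it does the opposite.

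**Working it through.** **Inputs.** The factor (2.14) and its units (mmol/L on both sides) come from SAP Section 5.3. The molar masses are physical constants that the documents do not give: urea, CO(NH2)2, 60.056 g/mol; its two nitrogen atoms, 2 × 14.007 = 28.014 g/mol.

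**Step 1: reproduce 2.14.** In mass units, urea / urea nitrogen = 60.056 / 28.014 = 2.144. This is the SAP's figure, and it is obtained only in mass units.

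**Step 2: the factor in mmol/L.** One urea molecule carries one pair of nitrogen atoms.

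- BUN expressed as urea (one N2 unit per molecule): urea = 1 × BUN.
- BUN counted as single nitrogen atoms: urea = 0.5 × BUN.

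Neither gives 2.14.

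**Step 3: effect of the rule as written.** Listed BUN = urea / 2.14 = 0.467 × urea. Against factor 1 the shortfall is 1 − 0.467 = 53%.

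| Urea (mmol/L) | Listed as BUN (mmol/L) |
|---|---|
| 5 | 2.34 |
| 7 | 3.27 |
| 10 | 4.67 |
| 15 | 7.01 |
| 20 | 9.35 |

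Against the single-atom convention the correct BUN would be 2 × urea. The listed value would then be 0.467 / 2 = 0.234 of it, which is 77% too low.

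**Step 4: one specimen followed both ways.**

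- Measured as BUN, 28 mg/dL: 28 × 10 / 28.014 = 10.0 mmol/L.
- Measured as urea, the same specimen is 28 × 2.144 = 60.0 mg/dL, and 60.0 × 10 / 60.056 = 10.0 mmol/L.
- The SAP rule lists the second as 10.0 / 2.14 = 4.67 mmol/L, beside 10.0 for the first.
- With 2.14 used in mass units: 60.0 / 2.14 = 28.0 mg/dL of BUN, which is 10.0 mmol/L. The factor is right there and wrong in mmol/L.

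**Step 5: range in which a high value would be hidden.** The listed value is at or below the upper limit of normal (ULN) whenever urea ≤ 2.14 × ULN, provided the limit is not rescaled. The documents give no ULN, so these limits are assumptions:

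| Assumed ULN (mmol/L) | Urea listed as not high up to (mmol/L) |
|---|---|
| 6.5 | 13.9 |
| 7.1 | 15.2 |
| 8.3 | 17.8 |

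**The case against.** The case for treating this as minor has several parts.

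- **Scope.** The rule governs a listing. Nothing shows that converted values feed CTCAE grades, worst-grade tables or shift tables, and no endpoint or test uses urea. This stands, and it limits the impact.
- **Flags.** Hiding a high value requires classification after conversion against an unconverted range. Section 2.8.3 does not say at which point the class is assigned, and the embedded grading file cannot be seen. This also stands: misclassification is possible but not shown. With a rescaled range, or with the original flag kept, the flag would be right. The listed number would still be wrong and not comparable with measured BUN.
- **Frequency.** The permission to use either test sits in the central laboratory collection plan. If the central laboratory runs one test throughout, mixing would come mainly from local results, which the protocol's second amendment allows exceptionally. The number of converted results is unknown. That affects how many entries are wrong, not whether the rule is.
- **Label slip.** The author may have meant mg/dL, and the program may already convert correctly. This is possible. However, the written units are mmol/L on both sides, so the text needs correction either way and the program needs checking.
- **Choice of factor.** The SAP does not state how BUN in mmol/L is expressed, so factor 1 rests on a convention. That is fair, and the correction should name the convention.

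The source cited for 2.14 was not available. The conclusion rests on molar masses, which no source can alter.

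**Conclusion.** The rule is wrong as written. The factor 2.14 holds in mass units only, and no molar convention yields it. Applied to mmol/L it lists each urea result at 47% of its value, a 53% understatement if BUN is expressed as urea and 77% if single nitrogen atoms are counted.

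That raised values can look normal is conditional on a normal range that is not rescaled, or on a reader comparing converted with measured BUN. The SAP excludes neither.

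The practical weight is modest: a safety listing is affected, not efficacy, and no grading or shift table is shown to be touched. It still merits correction because the error is certain in the text, the listing is where individual patients' renal values are read, and the 96-week analysis and any separate end-of-study-treatment analysis come after addendum 1.0, which is dated 14 October 2020.

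**What to change.** In Section 5.3, replace the rule with urea (mmol/L) = BUN (mmol/L), and state that BUN in mmol/L is expressed as urea. If 2.14 is kept, restrict it to conversion between mg/dL of urea and mg/dL of urea nitrogen, carried out before conversion to SI units. Add one sentence saying which normal range is used for a renamed urea result and whether the low/normal/high class is assigned before or after renaming.

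Then check which units and factor the listing program actually used. If it divided molar values by 2.14, correct the constant and rerun the listing and its flags, including any already produced for the primary analysis.

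The cost is one or two lines in the SAP and, if the program is affected, one constant plus re-verification of the listing. Rerunning output after the primary database lock is some extra work, but small.
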